### **5.3 Treatment Fidelity**

For the purposes of the study, therapists (who may or may not be employees at NCORP component sites) are considered to be research therapists and will contract (or subcontract) with the study to directly provide services for the research grant. As part of the contract, research therapists will be required to meet quality metrics including the audiotaping of psychotherapy sessions to ensure treatment fidelity. All therapy sessions will be audiotaped, and 8% of psychotherapy sessions (1 session per randomized participant) will be randomly selected for review (not live) by [name] using a measure of therapist adherence (Appendix 18) and competence developed and used by Stanley and colleagues (Stanley et al., 1996; Stanley et al., 2003). This measure assesses both the competence and adherence of the therapist in the delivery of the specific skills of the intervention (e.g., progressive muscle relaxation, problem solving, etc.) as well as an overall rating of therapist competence and adherence. Data suggest high internal consistency ( $\alpha = .91\text{-.94}$ ) and greater variability in ratings attributed to clinicians (29%) than raters (9%), suggesting good reliability of the instruments (personal communication, [name]; see Appendix 18 for a copy of this measure.)

Local site staff that are part of the research team and are responsible for making check-in calls with study participants will be audio-taped for adherence to study protocol and competence. All check-in calls will be audiotaped and 16% of calls (1 session per participant) will be randomly selected for review (not live) by [name] using a measure of adherence and competence developed for this study (see Appendix 19 for a copy of this measure.) [name] will meet via telephone with the research staff whose ratings indicate difficulties in intervention delivery.

Therapists (CBT)/research staff (check-in calls) who do not demonstrate competency (competency score  $< 6$ ) will receive additional training until competency is demonstrated. [name] will meet with therapists on a regular basis to discuss cases, review therapist adherence and competence ratings, and answer questions regarding protocol administration. Any areas of nonadherence will be reviewed, and the therapist will review any difficulties in intervention delivery.

The primary purpose of the data collected from the audiotaped therapy sessions and check-in calls is to identify research personnel who are not implementing the protocol/intervention with fidelity and to provide these personnel with additional supervision and/or training to improve protocol adherence. This is a common approach used in clinical trials of psychotherapy and behavioral interventions. The study will not use aggregate data from the audiotaped sessions/calls as a feasibility/adoption metric.

Study therapists will meet regularly with Drs. [name] or [name] for ongoing discussion of cases and study supervision.

## 5.4 Management of Study Risk

The following procedures are in place to protect against possible risks:

Participants who are at high risk for adverse outcomes (e.g., active suicidal ideation with plan and intent, current psychosis) will be excluded from the study. Participants who do not meet study inclusion criteria will be provided with alternative referrals. If any participant shows evidence of the need for immediate treatment (e.g., active psychosis, suicidal intent) at any time during the consent, assessment, and treatment periods, the participant will be referred for immediate psychiatric assistance (as specified in the Crisis Protocol, Appendix 21), and one of the co-PIs will be notified.

The only risk of this study is that some individuals may find discussing their problems with others to be uncomfortable, embarrassing, and/or stressful. This is expected to be temporary. All study staff will be trained to deal with these situations, and every effort will be made to address each participant's concerns or problems in the most supportive, empathic, and therapeutic manner.

## 5.5. Crisis Protocol

If any participant indicates a significant worsening in anxiety or depression scores (1 standard deviation increase (rounded to the nearest integer) on the GAD-7 (Change $\geq 4$ ) or PHQ-9 (Change $\geq 6$ ) from baseline) or the participant expressed suicidal ideation on the PHQ-9 (Question 9 score of >2), the computer software system will automatically generate an e-mail to the co-PIs and the Wake Forest School of Medicine Project Manager. The co-PIs or Project Manager will follow up with staff (either the therapists for participants in the high-intensity stepped-care telehealth or site personnel for participants in the low-intensity stepped-care telehealth or usual care arms) to enact the Crisis Protocol and complete a Crisis Protocol Event Form. During the course of a regularly scheduled participant contact, it may become evident that there is a need for immediate evaluation. (e.g., active suicidal ideation, active psychotic symptoms, disorientation). Staff will be instructed to follow the Crisis Protocol and complete the Crisis Protocol Event Form. In both cases, the participant may be referred for psychiatric care by their primary care physician or by an emergency department physician.

Study staff will follow the steps outlined in the Crisis Protocol and participants will receive information about safety precautions and procedures to follow in the event of a crisis (i.e., the participant becomes imminently suicidal). Because active suicidal ideation is an exclusion criterion for the study, we anticipate that the risk of participants becoming suicidal during the study will be minimal. Further, based on our prior studies, no participants randomized into the study became imminently suicidal. All study staff (therapists, site staff) will receive training on the Crisis Protocol and coping with participant distress that may be experienced during the consent, assessment and treatment procedures. In addition, sites will have regular study team meetings to discuss clinical issues. [name] will review the status and progress of participants with the study therapists on a regular (at least monthly) basis. All participants will be contacted at Week 7 to assess the primary outcomes and depressive symptoms. Additionally, study therapists will attempt to reach participants who miss a session by calling the participant twice in a one-week period. If the therapist is unable to contact the participant by phone, the therapist will send the participant a letter by mail with a request that the participant contact the therapist regarding interest in continuing the study sessions.

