In accordance with ASCO guidelines, participants with no/mild symptoms will be provided with written survivorship resources (a letter that contains a link to the National Cancer Institute booklet "Facing Forward: Life after Cancer Treatment") and will not be randomized (Appendix 20). Participants with either moderate or severe distress (anxiety or depressive symptoms) will be randomized into stepped-care telehealth (tailored to level of symptoms) or EUC. For participants with moderate symptoms (PHQ-9: 8-14; GAD-7: 10-14), low-intensity stepped-care telehealth will consist of a self-guided cognitive behavioral therapy (CBT) workbook to reduce anxiety and depressive symptoms and biweekly (every two weeks) check-in calls from research staff at NCORP components. On the biweekly check-in calls, research staff from NCORP components will provide minimal support and will administer the scripted "Telephone Script/Manual for Low-Intensity Group Check-in Call Form." This form assesses changes in symptom severity during the past two weeks. The site staff person is directed to follow Telehealth crisis protocol, refer to Appendix 21, for participants indicating "thoughts of death or suicidal ideation." Site staff should also follow crisis procedures for any other problems identified during administration of the form where follow-up is needed.

For participants with severe symptoms (PHQ-9: 15-27; GAD-7: 15-21), high intensity stepped-care telehealth will consist of a CBT workbook with accompanying psychotherapy by a Master's- or doctoral-level therapist delivered by telephone. Participants randomized to EUC will receive survivorship resources (Appendix 20) and referral information for local mental health providers.

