## Study Parameter Table

	Recruitment/ Chart Review	Pre-Screen	Verbal Consent	Full Screen	Full Informed Consent	Baseline	Enrollment/ Randomization (wk0)	Weeks 1-13			Post Week 13
								Wk1 or 2	W7	W13	
NCORP Component Site Staff Responsibility											
Mail Recruitment Documentation*	As needed										---
Pre-Visit Form (Appx 2)	X										---
Pre-Screening Form (Appx 3)*		X a									---
Abbreviated Verbal Consent			X a								---
Screening Form (Appx 4)*				X a							---
Full Informed Consent					X a						---
Baseline Self-Report Letter and Measures (Appxs 5a+b)*						X a					---
Baseline Interviewer-Administered Measures and Chart Review (Appx 6)*							X a				---
Letter to Ineligible Participants (SD 2)		As Needed									---
Enrollment Form (Appx 7)							X				---
Randomization Form (Appx 8)							X b				---
EUC Randomization*							X		X		EUC
Expectancy Rating Scale and Letter  (Appxs 10a+b)							X				LISC/ HISC
Low Intensity Check-In Call Form (Appx 14)								Biweekly (wks 2/4/6/8/10/12)			LISC
Upload audio recordings								Biweekly (wks 2/4/6/8/10/12)			LISC
Week 7 Mid-Assessment Interviewer-Administered Measures (Appx 11)*									X		All
Week 13 Self-Report Letter and Measures (Appxs 12a+b)*										X	All
Week 13 Interviewer-Administered Measures (Appx 13)*										X c	All
Participant Completion Letter (SD 3)/Resource Sheet (SD 9)										X	LISC/ HISC
Participant Change Status Form (Appx 23)								As Needed			All
Adverse Event Form (Appx 22)		As Needed									All
Crisis Protocol Event Form (Appx 21)		As Needed									All
Tracking Log (Appx 24)		To be completed for each attempted contact and actual contact									All
Wake Forest Research Base Responsibility											
EUC Randomization*							X				EUC
Investigator adherence rating forms (Appx 18 and 19)*								As needed			LISC/ HISC
Mail Recorder							As needed				LISC/ HISC
Mail CBT Booklet							X				LISC/ HISC
Mail CBT Booklet										X	EUC
Study Therapist Responsibility											
Weekly Therapist activities (Appxs 15-17) recordings*								Weekly (wks 1-13)			HISC
Tracking log		To be completed for each attempted contact and actual contact									HISC

Abbreviations: Appx=Appendix, EUC=Enhanced Usual Care, HISC=High-Intensity Stepped-Care Arm, LISC=Low-Intensity Stepped-Care Arm

\* See appendix 26 for details

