a If participant is being seen in person, all of these steps can occur during one appointment

b Randomization should happen within 30 days of the full screen. If not, full screen (appx 4) will need to be re-administered

c For participants in the HISC arm, week 13 measures should be completed after the intervention is finished (could be weeks 13-15)

**Note:** Regarding potential participant burden, estimated times to complete study measures are as follows: pre-screen (5-10 minutes); screen (up to 20 minutes); participant measures at baseline and Week 13 (30-60 minutes); participant measures at Week 7 (5 minutes)

**Note:** See the Telehealth website for specific windows of when data should be collected post-randomization for each participant. The PHQ-9 and GAD-7 must be entered into the Telehealth website within 48 hours of administration. All other assessments should be entered within 14 days of the date assessments are completed unless otherwise specified.

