### 8.2 Secondary Endpoints

#### 8.2.1. Depression and Anxiety Measures

The **PHQ-9** is a self-report measure of DSM-IV symptoms of Major Depressive Disorder. Participants rate how often they have experienced nine symptoms over the past 2 weeks on a scale of 0 (not at all) to 3 (nearly every day). Responses are summed, with higher scores indicating greater depressive symptomatology. It has demonstrated good reliability and validity. The traditional cutoff for the PHQ-9 is a score  $\geq 10$ . However, ASCO guidelines recommend using a score  $\geq 8$ , based on a study of cancer outpatients and a meta-analysis of use of the PHQ-9 for identifying depression in cancer patients.

The **GAD-7** is a self-report measure of DSM-IV symptoms of GAD. Participants rate 7 questions on a scale of 0 (not at all) to 3 (nearly every day); one additional question assesses the interference of these symptoms with functioning. The first 7 questions are summed to create a total score. It has been validated for use in the general population and in primary care. The GAD-7 has demonstrated good sensitivity (89%) and specificity (82%) in identifying GAD diagnoses when using a cut point of 10. It also has good internal consistency (alphas = 0.89-0.92) and test-retest reliability (intraclass correlation = .83).

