## **11.3 Selected Adverse Events**

A select list of adverse events include suicide attempts, psychosis, worsening anxiety, worsening depression, and suicidal ideation, should be reported as an adverse event, regardless of whether they resulted in an ER visit or hospitalization.

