### **11.3.1. Definition of Worsening Anxiety or Depression**

An adverse event form should be completed for any participant who indicates a significant worsening in anxiety or depression scores (1 standard deviation increase (rounded to the nearest integer) on the GAD-7 (Change $\geq 4$ ) or PHQ-9 (Change $\geq 6$ ) from baseline). The computer software system will automatically generate an e-mail to the co-PIs and the project manager. If there is a need for immediate treatment (e.g., active suicidal ideation, active psychotic symptoms, disorientation, and active substance abuse) at any point in time, staff persons will notify the co-PIs. In both cases, the participant may be referred for psychiatric care.

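### The automatic suicidal-ideation alert in section 5.5 fires only at the top PHQ-9 Question 9 score, leaving scores of 1 and 2 without a score-based rule

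*Combined protocol and SAP*

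**What the plan says.** Section 5.5 lists three triggers for an automatic e-mail to the co-PIs and project manager: a GAD-7 rise of at least 4 from baseline, a PHQ-9 rise of at least 6, or that "the participant expressed suicidal ideation on the PHQ-9 (Question 9 score of >2". Those who receive it then have the therapist or site staff enact the Crisis Protocol. Section 8.2.1 says that participants rate "nine symptoms over the past 2 weeks on a scale of 0 (not at all) to 3 (nearly every day".

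Other parts of the plan bear on the same event:

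- **Section 3, low-intensity check-in calls.** "The site staff person is directed to follow Telehealth crisis protocol, refer to Appendix 21, for participants indicating" that they have been thinking about death or suicide. No score is attached.
- **Section 11.3.** "worsening anxiety, worsening depression, and suicidal ideation, should be reported as an adverse event", with no threshold for ideation. Section 11.3.1 does put numbers on worsening ("An adverse event form should be completed for any participant who indicates a significant worsening in anxiety or depression scores", using the same +4 and +6), but it does not define ideation.
- **Section 5.5, second route.** "During the course of a regularly scheduled participant contact, it may become evident that there is a need for immediate evaluation"; staff then follow the Crisis Protocol directly. Sections 5.4 and 11.3.1 also have a co-PI notified when immediate treatment is needed.
- **Study Parameter Table.** Low-intensity calls are "Biweekly (wks 2/4/6/8/10/12" and therapist contact in the high-intensity arm is weekly. EUC participants are scheduled for assessment after randomization only at Weeks 7 and 13. A note adds: "The PHQ-9 and GAD-7 must be entered into the Telehealth website within 48 hours of administration".

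**The concern.** Section 5.5 treats Question 9 as the PHQ-9's measure of suicidal ideation, then sets a cut-off that only the highest answer can pass. A participant who scores 1 or 2 has given a positive answer to that question, yet the software stays silent unless a total score has also worsened sharply. Elsewhere the plan sets no minimum: a low-intensity participant who mentions such thoughts on a call starts the crisis protocol, and ideation is reportable as an adverse event.

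At stake is whether a positive Question 9 answer is reviewed by a defined rule or left to the interviewer's impression. The trial recruits people for anxiety and depressive symptoms, plans 40 of its 90 participants in the severe stratum (section 13.2), and excludes active ideation only when there is plan and intent (4.2.7). Participants with lesser ideation can therefore be enrolled.

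**Working it through.** **1. Reproduce the thresholds in 5.5.** Section 13.3 gives SDs of change of 5.8 (PHQ-9) and 4.2 (GAD-7). Rounded to integers these are 6 and 4, which match the worsening triggers. The item 9 cut-off has no stated derivation.

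**2. Which Question 9 scores trigger the e-mail.** Possible scores are 0, 1, 2 and 3.

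| Rule | Scores that trigger | Positive scores missed |
|---|---|---|
| >2 (as written) | 3 | 1 and 2 (two of three) |
| ≥2 | 2, 3 | 1 |
| ≥1 | 1, 2, 3 | none |

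The documents do not show whether ≥2 was meant. Even that reading misses a score of 1.

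**3. Whether the total-score alerts fill the gap.**

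- If Question 9 rises from 0 to 2, it supplies 2 of the 6 points needed. The other eight items must show a net rise of at least 6 − 2 = 4. If it rises from 0 to 1, they must rise by at least 5.
- The PHQ-9 maximum is 9 × 3 = 27. A rise of 6 needs a baseline of 27 − 6 = 21 or less, so it is impossible from 22-27, which is 6 of the 13 integer values in the severe range 15-27.
- The GAD-7 maximum is 7 × 3 = 21. A rise of 4 needs a baseline of 21 − 4 = 17 or less, so it is impossible from 18-21, which is 4 of the 7 values in 15-21.
- For a participant in both upper ranges, a Question 9 score of 3 is the only automatic trigger left.

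These fractions count score values, not participants. The documents give no distribution of baseline scores.

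**4. Where the e-mail carries most weight.** High-intensity participants have weekly therapist contact and low-intensity participants have six scheduled calls. EUC is planned at 45 participants, about 40/2 = 20 of them severe under equal allocation, with scheduled assessments nominally 13 − 7 = 6 weeks apart. Section 12.4 mentions check-in calls for EUC, but the Study Parameter Table schedules none.

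**The case against.** The strongest reply is that the e-mail is a backstop to a live contact. Site staff administer the PHQ-9 by telephone at Weeks 7 and 13 and complete the adverse event ascertainment form at the same visits (sections 7.6, 7.7 and 11.1). All staff are trained on the Crisis Protocol. Section 5.4 requires referral and co-PI notification for any participant who shows a need for immediate treatment, and 5.5 and 11.3.1 say much the same without requiring a score. This stands, and it narrows the point considerably.

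It can also be said that an urgent e-mail, a scripted action on a call and an adverse event record serve different purposes and need not share a threshold. That is fair: the three rules are out of line rather than in strict contradiction. Nor can it be shown that the low-intensity call form uses Question 9, since Appendix 14 was not available.

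A reader might infer that an EUC participant who scores 1 or 2 at Week 7 gets no required follow-up before Week 13, or that what reaches the DSMB is altered. The documents support neither. The staff-judgement route applies at every contact, section 11.3 already covers ideation without a threshold, and the crisis steps and adverse event questions sit in Appendices 21 and 22, which were not supplied and may set a lower bar.

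The reply leaves one thing unanswered. None of these safeguards says what to do with a score of 1 or 2 when the interviewer sees no immediate need.

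**Conclusion.** The point holds in this bounded form. As written, the item 9 alert responds to one of three positive scores, and the total-score alerts cannot be relied on for the other two, least of all in participants with the highest baseline scores. The supplied text has no score-based rule for scores of 1 or 2 when no urgent need is apparent, and EUC, with the fewest scheduled contacts, depends most on the alert.

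The conclusion rests on the 0-3 item scoring, the wording of 5.5 and the Study Parameter Table. It needs no assumption about how common ideation will be; the number of participants affected cannot be derived from the documents and would be zero if every positive answer were a 3. If Appendix 21 sets a lower threshold, the remaining fault is that 5.5 disagrees with it. This is a participant-safety and consistency matter and does not touch the feasibility endpoints, the efficacy analyses or the sample size.

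**What to change.** **Section 5.5.** Set the Question 9 trigger at ≥1 at Weeks 7 and 13 in every arm. Have the interviewer ask about plan and intent on the same call, because the e-mail depends on data entry that may come up to 48 hours later. If plan or intent is present, refer immediately under 5.4; otherwise notify a co-PI.

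**Section 11.3.** Report as an adverse event ideation that is new or increased from the Question 9 score at screening, and any new plan, intent or behaviour. Reporting every score of 1 or more would log ideation that was present at entry and has not changed, which sits badly with the change-from-baseline approach in 11.3.1.

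If >2 is deliberate, the plan should say why and name who reviews scores of 1 and 2. Appendices 21 and 22 should be checked for agreement with whatever is chosen.

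**Cost.** One software threshold, a short scripted follow-up, revised wording in two sections and briefing of site staff. Question 9 is already collected at both visits. There will be some extra brief follow-ups, including for unchanged ideation; their number cannot be estimated from the documents. Enrolment, endpoints and sample size stay as they are.

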### 5.5.1. Emergency Contacts

As an additional safety precaution and part of the screening, participants will provide the names of two emergency contacts and their phone numbers. Study staff will contact the emergency contacts if needed during the administration of the Crisis Protocol or in any other emergency. If the Crisis Protocol is activated during a study session or contact and the participant misses the next scheduled session, then the therapist will call the emergency contacts immediately.

## 6. REGISTRATION

### 6.1 Investigator and Research Associate Registration with CTEP

Food and Drug Administration (FDA) regulations and National Cancer Institute (NCI) policy require all individuals contributing to NCI-sponsored trials to register and to renew their registration annually. To register, all individuals must obtain a Cancer Therapy Evaluation Program (CTEP) Identity and Access Management (IAM) account (<https://ctepcore.nci.nih.gov/iam>). In addition, persons with a registration type of Investigator (IVR), Non-Physician Investigator (NPIVR), or Associate Plus (AP) must complete their annual registration using CTEP's web-based Registration and Credential Repository (RCR) <https://ctepcore.nci.nih.gov/rrc>.

RCR utilizes five person registration types.

- IVR — MD, DO, or international equivalent;
- NPIVR — advanced practice providers (e.g., NP or PA) or graduate level researchers (e.g., PhD);
- AP — clinical site staff (e.g., RN or CRA) with data entry access to CTSU applications such as the Roster Update Management System [RUMS], OPEN, Rave, acting as a primary site contact, or with consenting privileges;
- Associate (A) — other clinical site staff involved in the conduct of NCI-sponsored trials; and
- Associate Basic (AB) — individuals (e.g., pharmaceutical company employees) with limited access to NCI-supported systems.

RCR requires the following registration documents:

Documentation Required	IVR	NPIVR	AP	A	AB
FDA Form 1572	✓	✓			
Financial Disclosure Form	✓	✓	✓		
NCI Biosketch (education, training, employment, license, and certification)	✓	✓	✓		
GCP training	✓	✓	✓		
Agent Shipment Form (if applicable)	✓				
CV (optional)	✓	✓	✓		

An active CTEP-IAM user account and appropriate RCR registration is required to access all CTEP and CTSU (Cancer Trials Support Unit) websites and applications. In addition, IVRs and NPIVRs must list all clinical practice sites and Institutional Review Boards (IRBs) covering their practice sites on the FDA Form 1572 in RCR to allow the following:

- Addition to a site roster
- Assign the treating, credit, consenting, or drug shipment (IVR only) tasks in OPEN
- Act as the site-protocol Principal Investigator (PI) on the IRB approval; and
- Assign the Clinical Investigator (CI) role of the Delegation of Tasks Log (DTL)

In addition, all investigators act as the Site-Protocol PI (investigator listed on the IRB approval), consenting/treating/drug shipment investigator in OPEN, or as the CI on the DTL must be rostered at the enrolling site with a participating organization.

Additional information is located on the CTEP website at <https://ctep.cancer.gov/investigatorResources/default.htm>. For questions, please contact the RCR Help Desk by email at [[contact]](mailto:[contact]).

